**Table 2: Table of Events (Years 2 to 4)**

	Optional Open-label Extension Phase												Observational FU Visit (4 weeks $\pm$ 7 days after last dose) a	Early Termination (ET) b
Year	Year 2				Year 3				Year 4 c					
Visit Number	16	17	18	19	20	21	22	23	24	25	26	27		
Week	76	88	100	112	124	136	148	160	172	184	196	208		
Day	533 $\pm$ 7	617 $\pm$ 7	701 $\pm$ 7	785 $\pm$ 7	869 $\pm$ 7	953 $\pm$ 7	1037 $\pm$ 7	1121 $\pm$ 7	1205 $\pm$ 7	1289 $\pm$ 7	1373 $\pm$ 7	1457 $\pm$ 7		
Prior/Concomitant Medications	X	X	X	X	X	X	X	X	X	X	X	X	X	X
Safety Assessments														
Adverse Events	X	X	X	X	X	X	X	X	X	X	X	X	X	X
Vital signs d	X	X	X	X	X	X	X	X	X	X	X	X	X	X
Limited Physical Examination e	-	X	-	-	-	X	-	-	-	X	-	-	-	-
Complete Physical Examination f	-	-	-	X	-	-	-	X	-	-	-	X	X	X
Weight	X	X	X	X	X	X	X	X	X	X	X	X	X	X
Hematology g	-	X	-	X	-	X	-	X	-	X	-	X	X	X
Serum Chemistry h	-	X	-	X	-	X	-	X	-	X	-	X	X	X
Pregnancy Testing i	-	-	-	-	-	-	-	-	-	-	-	X	X	X
Investigational Product														
Dispense IP	X	X	X	X	X	X	X	X	X	X	X	X	-	-
IP Accountability	X	X	X	X	X	X	X	X	X	X	X	X	-	-

BD = Behçet's disease; ET = Early Termination; FCBP = female of child-bearing potential; FU = follow-up; IP = investigational product.

a Observational Follow-up Visit - Subjects who discontinue at any time from the study for any reason and subjects who do not choose to enter the optional Open-label Extension Phase are to enter the 4-week Posttreatment Observational Follow-up Phase.

b ET assessments are to be completed when a subject withdraws at any time from the Extension study.

c After Year 4 – if apremilast is not commercially available the visits will repeat starting at Visit 16 until apremilast is commercially available for BD or until the benefit/risk of apremilast is found not to be acceptable for BD, according to either the sponsor or health authority.

- d Vital signs include temperature, pulse, respiratory rate, and seated blood pressure.
- e Limited physical examinations will include evaluations to assess the subject's BD. If a subject presents with symptoms other than BD, the Investigator should determine whether a complete physical examination should be performed.
- f Complete physical examinations will include weight (street clothes; no shoes), skin, nasal cavities, eyes, ears, lymph nodes, genitalia, and respiratory, cardiovascular, gastrointestinal, neurological and musculoskeletal systems evaluations.
- g See [Section 6.6.7.1](#) for details.
- h See [Sections 6.6.7.2](#) and [6.6.7.4](#) for details.
- i A urine pregnancy test(s) should be administered if the FCBP subject misses a menstrual period. If a FCBP terminates the study early, a serum pregnancy test will be completed after the last dose of IP.

## **6. PROCEDURES**

Assessments, as detailed in the following sections, will be done at the intervals specified in the Table of Events, [Section 5](#).

### **6.1. Informed Consent**

An Informed Consent Document must be signed before any study related assessments are performed.

### **6.2. Demographic Data**

The demographic data will include (but not be limited to) the subject's initials (as allowed per local regulations), date of birth (as allowed per local regulations), age, gender, and race/ethnic origin. The demographic profile will be recorded in the source documents and electronic case report form (eCRF).

### **6.3. Complete Medical History**

Relevant medical history should be recorded, including previous relevant surgeries. History of BD will be reported in the eCRF including diagnosis date and a detailed history of BD manifestations, as listed in [Appendix A](#), and BD treatment history.

### **6.4. Inclusion/Exclusion Criteria**

Subjects must meet all inclusion criteria ([Section 7.2](#)) and must not have any of the conditions specified in the exclusion criteria ([Section 7.3](#)). The subject's source documents must support his/her qualifications for the study (eg, if a female subject does not require pregnancy testing and birth control because of a hysterectomy, the date of the hysterectomy must be included in the medical history).

### **6.5. Prior and Concomitant Medications**

All medications and therapies (including systemic and topical medications, prescription, and non-prescription, including herbal supplements) taken by the subject up to 30 days prior to Visit 1 should be recorded, including the stop dates for medications prohibited in the study, at the time of consent.

Previous biologic use should be recorded, including start and stop dates regardless of when it was administered.

All medications and therapies being taken by the subjects, at any time during the study, must also be recorded.

### **6.6. Safety Assessments**

The following safety assessments will be performed as outlined in [Section 5](#).

### **6.6.1. Adverse Events**

The time frames for recording all AEs are indicated in [Section 5](#). It should be noted that during the first 64 weeks of the study worsening of a subject's BD should be considered as worsening of the disease under study, and should not be captured as an AE. Worsening of disease will be captured on a separate BD activity page in the eCRF that lists each of the BD manifestations.

Worsening of a subject's BD will be captured on the AE eCRF for subjects who continue in the optional Open-label Extension Phase after Week 64.

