#### **6.6.5. Vasculitis Assessment**

The PDE4 inhibitors, including apremilast, have been shown to produce inflammatory perivascular histopathological changes in animal studies (eg, rodent toxicology studies). The Investigator should be watchful for any signs and symptoms of vasculitis at all times. Any suspicion of vasculitis must be thoroughly investigated by taking pertinent subject history, doing a physical examination, reviewing AEs, and performing diagnostic procedures as clinically indicated. A subject with signs and symptoms of possible vasculitis should receive a thorough evaluation as described above, managed as medically appropriate, and continued with follow-up until the signs and symptoms of vasculitis have resolved. If vasculitis is assessed as being BD-related, then the vasculitis should be reported on the BD activity pages in the eCRF.

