### **10.9. Other Topics**

## 11. ADVERSE EVENTS

### 11.1. Monitoring, Recording and Reporting of Adverse Events

An adverse event (AE) is any noxious, unintended, or untoward medical occurrence that may appear or worsen in a subject during the course of a study. It may be a new intercurrent illness, a worsening concomitant illness, an injury, or any concomitant impairment of the subject's health, including laboratory test values (as specified by the criteria in [Section 11.3](#)), regardless of etiology. Any worsening (ie, any clinically significant adverse change in the frequency or intensity of a pre-existing condition) should be considered an AE. A diagnosis or syndrome should be recorded on the AE page of the eCRF rather than the individual signs or symptoms of the diagnosis or syndrome.

Worsening of a subject's BD (any manifestation) should be considered as worsening of disease under study, and should not be captured as an AE, unless the event meets the definition of an SAE. Worsening of disease will be reported on the BD activity pages that lists each of the BD manifestations in the eCRF, and not captured in the AE eCRF. See [REDACTED] for more details.

Worsening of a subject's BD will be captured on the AE eCRF for subjects who continue in the optional Open-label Extension Phase after Week 64. Abuse, withdrawal, sensitivity or toxicity to an investigational product should be reported as an AE. Overdose, accidental or intentional, whether or not it is associated with an AE should be reported on the overdose eCRF (see [Section 8.3.2](#) for the definition of overdose). Any sequela of an accidental or intentional overdose of an investigational product should be reported as an AE on the AE eCRF. If the sequela of an overdose is an SAE, then the sequela must be reported on an SAE report form and on the AE eCRF. The overdose resulting in the SAE should be identified as the cause of the event on the SAE report form and in the eCRF but should not be reported as an SAE itself.

In the event of overdose, the subject should be monitored as appropriate and should receive supportive measures as necessary. There is no known specific antidote for apremilast overdose. Actual treatment should depend on the severity of the clinical situation and the judgment and experience of the treating physician.

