All subjects will be monitored for AEs during the study. Assessments may include monitoring of any or all of the following parameters: the subject's clinical symptoms, laboratory, pathological, radiological or surgical findings, physical examination findings, or findings from other tests and/or procedures.

All AEs will be recorded by the Investigator from the time the subject signs informed consent until 28 days after the last dose of IP and those SAEs made known to the investigator at any time thereafter that are suspected of being related to IP. All AEs and SAEs will be recorded on the AE page of the CRF and in the subject's source documents. All SAEs must be reported to Celgene Drug Safety within 24 hours of the Investigator's knowledge of the event by facsimile, or other appropriate method, using the SAE Report Form, or approved equivalent form.

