### 11.2.1. Seriousness

A serious adverse event (SAE) is any AE occurring at any dose that:

- Results in death;
- Is life-threatening (ie, in the opinion of the Investigator, the subject is at immediate risk of death from the AE);
- Requires inpatient hospitalization or prolongation of existing hospitalization (hospitalization is defined as an inpatient admission, regardless of length of stay);
- Results in persistent or significant disability/incapacity (a substantial disruption of the subject's ability to conduct normal life functions);
- Is a congenital anomaly/birth defect;
- Constitutes an important medical event.

Important medical events are defined as those occurrences that may not be immediately life threatening or result in death, hospitalization, or disability, but may jeopardize the subject or require medical or surgical intervention to prevent one of the other outcomes listed above. Medical and scientific judgment should be exercised in deciding whether such an AE should be considered serious.

Events **not considered** to be SAEs are hospitalizations for:

- A standard procedure for protocol therapy administration. However, hospitalization or prolonged hospitalization for a complication of therapy administration will be reported as an SAE.
- Routine treatment or monitoring of the studied indication not associated with any deterioration in condition.
- A procedure for protocol/disease-related investigations (eg, surgery, scans, endoscopy, sampling for laboratory tests, bone marrow sampling). However, hospitalization or prolonged hospitalization for a complication of such procedures remains a reportable SAE.
- Hospitalization or prolongation of hospitalization for technical, practical, or social reasons, in absence of an AE.
- A procedure that is planned (ie, planned prior to starting of treatment on study); must be documented in the source document and the CRF. Hospitalization or prolonged hospitalization for a complication remains a reportable SAE.
- Emergency outpatient treatment or observation that does not result in admission, unless fulfilling other seriousness criteria above.

If an AE is considered serious, the AE screen of the eCRF and the SAE Report Form must be completed.

For each SAE, the Investigator will provide information on severity, start and stop dates, relationship to IP, action taken regarding IP, and outcome.

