## **11.5. Reporting of Serious Adverse Events**

Any AE that meets any criterion for an SAE requires the completion of an SAE Report Form in addition to being recorded on the AE page/screen of the CRF. All SAEs must be reported to Celgene Drug Safety within 24 hours of the Investigator's knowledge of the event by facsimile, or other appropriate method, using the SAE Report Form, or approved equivalent form. This instruction pertains to initial SAE reports as well as any follow-up reports.

The Investigator is required to ensure that the data on these forms is accurate and consistent. This requirement applies to all SAEs (regardless of relationship to IP) that occur during the study (from the time the subject signs informed consent until 28 days after the last dose of IP) or any SAE made known to the Investigator at any time thereafter that are suspected of being related to IP. Serious adverse events occurring prior to treatment (after signing the Informed Consent Form) will be captured.

The SAE report should provide a detailed description of the SAE and include a concise summary of hospital records and other relevant documents. If a subject died and an autopsy has been performed, copies of the autopsy report and death certificate are to be sent to Celgene Drug Safety as soon as these become available. Any follow-up data should be detailed in a subsequent SAE Report Form, or approved equivalent form, and sent to Celgene Drug Safety.

Where required by local legislation, the Investigator is responsible for informing the Institutional Review Board/Ethics Committee (IRB/EC) of the SAE and providing them with all relevant initial and follow-up information about the event. The Investigator must keep copies of all SAE information on file including correspondence with Celgene and the IRB/EC.

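### Protocol 6.6.1 keeps all Behçet's worsening out of adverse event capture for 64 weeks, while 11.1 excepts serious events; the two sections need reconciling so that sites report serious flares consistently

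*Protocol*

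**What the plan says.** Three places in the protocol deal with where worsening of BD is recorded.

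- **Section 6.6.1 (Adverse Events).** The rule applies "during the first 64 weeks of the study". Worsening in that time "should not be captured as an AE. Worsening of disease will be captured on a separate BD activity page" of the eCRF. No exception is given for serious events, and there is no pointer to Section 11.
- **Section 11.1 (Monitoring, Recording and Reporting of Adverse Events).** Worsening of any manifestation "should not be captured as an AE, unless the event meets the definition of an SAE". The next sentence sends worsening to the BD activity pages, "and not captured in the AE eCRF", without restating the exception. It is followed by a cross-reference that is redacted in the public copy.
- **Section 6.6.5 (Vasculitis Assessment).** "If vasculitis is assessed as being BD-related, then the vasculitis should be reported on the BD activity pages in the eCRF". It does not say what happens if that vasculitis is serious.

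Sections 6.6.1 and 11.1 agree that, in the open-label extension after Week 64, worsening goes on the AE page.

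**The concern.** For a flare that leads to hospital admission, or a serious vascular or neurological manifestation, 6.6.1 and 11.1 give different instructions over the same 64 weeks. Under 6.6.1 the event is not an AE. Under 11.1 it is an AE, an SAE, and reportable within 24 hours.

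Two things depend on which section a site follows. One is the sponsor's timely knowledge of serious events. The other is the completeness of the SAE comparison between arms. Section 1.3 reports Behçet's syndrome/flare as the most common TEAE on placebo in the Phase 2 study and the third most common on apremilast. Disease worsening is therefore a category of event in which the arms may differ, and uneven capture of its serious part would blur a comparison that readers will look at even though it is descriptive only.

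Vasculitis deserves particular care. Section 6.6.5 itself raises it as a concern for the drug class on the strength of animal findings, and it is also a manifestation of the disease.

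**Working it through.** There is no figure in the plan to reproduce and no arithmetic applies. The check sets the passages side by side and follows one event through them: a BD flare in the first 64 weeks that meets a seriousness criterion.

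1. **Is it an AE?** Section 6.6.1: no, without exception. Section 11.1: yes, because the exclusion does not apply to a serious event; the operative words are "should not be captured as an AE, unless the event meets the definition of an SAE".
2. **Is it an SAE?** Section 11.2.1: "A serious adverse event (SAE) is any AE occurring at any dose that" meets one of the listed criteria. An SAE is thus a subset of AEs. If step 1 was answered from 6.6.1, the event never enters that set. If it was answered from 11.1, it does. The 11.1 wording is slightly circular, since it makes AE status depend on SAE status while 11.2.1 makes SAE status depend on AE status, but its intent is clear.
3. **Is the SAE form required?** Section 11.5: "Any AE that meets any criterion for an SAE requires the completion of an SAE Report Form", in addition to the entry on the AE page. The starting point is again an AE.
4. **Is it reported in 24 hours?** Section 11.1: "All SAEs must be reported to Celgene Drug Safety within 24 hours". Section 11.5 adds that this holds whatever the relationship to study drug. It applies only to events that passed steps 1 and 2.
5. **Does it reach the safety tables?** SAP 4.2.6.1 defines a TEAE as a kind of AE. SAP 11.2.6 tabulates serious TEAEs and lists serious AEs. The visible SAP text describes no safety summary of post-baseline entries on the BD activity pages.

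| Step | Site applying 6.6.1 alone | Site applying Section 11 |
|---|---|---|
| Entry on BD activity page | Yes | Yes |
| Captured as AE | No | Yes |
| SAE form and 24-hour report | Could be missed | Required |
| Serious TEAE tables | Could be missed | Included |

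The sections therefore differ for exactly one class of event, serious worsening of BD up to Week 64. They agree on non-serious worsening and on the extension phase.

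**The case against.** The case on the other side is substantial.

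- **Section 11 governs reporting and states the exception.** It requires all SAEs within 24 hours. Section 11.2.1 exempts hospital stays for routine care of the studied indication only where there has been no deterioration, so an admission for a flare is not exempt. Section 16.1 has AE and SAE reporting reviewed with the investigator before enrolment, and SAE documentation verified at monitoring. A serious flare is missed only if a site reads 6.6.1 in isolation and monitoring does not catch it. This stands, and it limits the point to inconsistent practice.
- **The event is not lost.** A reader might infer from 6.6.1 that serious flares go unrecorded. They do not: the same sentence sends them to the BD activity page. What is at risk is their status as AEs and SAEs.
- **Section 6.6.5 does not bar AE capture.** A reader might take it as a second prohibition. It only names a place to report BD-related vasculitis and is compatible with 11.1. It is silent on serious cases, which calls for clarification and is not a contradiction.
- **The follow-on sentence in 11.1 can be read as describing only non-serious worsening.** That is the natural reading, coming straight after the exception. It is still worth making explicit.
- **Part of the text is redacted.** The cross-reference in 11.1 may lead to further guidance. It could help a site that reads Section 11, but it does not change the unqualified wording of 6.6.1.
- **Monitoring.** A reader might infer that such events would escape the Data Monitoring Committee. The documents do not show this. Section 4.1.2 gives the committee both safety and efficacy data under a charter that is not included. Section 4.1.1 lists what the internal safety team reviews without naming the BD activity pages, but that does not establish that they are withheld.

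**Conclusion.** The inconsistency is confirmed on the wording. Section 6.6.1 excludes all BD worsening from AE capture through Week 64; Section 11.1 excludes only worsening that is not serious. Because the SAE definition and the SAE form both start from an AE, a site relying on 6.6.1 alone could leave a serious flare out of 24-hour reporting and out of the serious TEAE tables, while still recording it on the BD activity page. It should be corrected, because the sponsor's own exception is missing where it is needed.

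The size cannot be estimated. It is tempting to scale the Phase 2 experience in Section 1.3, where 3 placebo and 2 apremilast subjects had serious TEAEs, to 102 per arm. Two quantities needed for this are not in the documents: the share of those events that were BD manifestations, and the fraction of sites that would apply 6.6.1 without Section 11. The second could be zero. The present trial also excludes active major organ involvement (Section 7.3), which bears on how often serious manifestations would arise. No count is offered.

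The conclusion rests on the visible text, with one cross-reference in 11.1 and parts of the SAP redacted.

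**What to change.** Reconcile the passages around the exception that Section 11.1 already contains:

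1. In 6.6.1, repeat the SAE exception or refer explicitly to 11.1.
2. In 6.6.5, state that entering BD-related vasculitis on the BD activity pages does not replace AE and SAE reporting when the event is serious.
3. In 11.1, limit the sentence that keeps worsening off the AE page to non-serious worsening.
4. Before the Week 12 lock, check BD activity page records against the SAE criteria while blinded to treatment, and query sites on any candidate event without an SAE report. Since the rule runs to Week 64, repeat the check before the later locks listed in SAP Section 2.

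The cost is a sentence or so in each of three sections, a memo to sites, and a reconciliation query. The reported SAE count may rise slightly. No endpoint, sample size or efficacy analysis changes.

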#### **6.6.1.1. Adverse Events of Special Interest**

The PDE4 inhibitors, including apremilast, have been associated with AE reports of diarrhea. Diarrhea has not been well characterized in previous apremilast studies.

Diarrhea is the passage of three or more loose or liquid stools per day, or more frequently than is normal for the individual (World Health Organization [[WHO](#)], 2013). Following the definition of diarrhea by the WHO and taking a more conservative approach, the AE of diarrhea in this protocol is defined as having two or more watery/liquid stools in a day.

In order to better characterize diarrhea and to distinguish similar events coding to the Medical Dictionary of Regulatory Activities (MedDRA) preferred term of diarrhea, subjects reporting diarrhea or similar events (eg, frequent bowel movements, loose bowels, etc.) will be asked whether they have had two or more watery/liquid stools in a day. Subjects who respond "yes" to this question will be further asked how often, on average, since their last visit have they experienced two or more watery/liquid stools in a day. Subjects who respond "no" to the question will not be asked any further questions.

### **6.6.2. Vital Signs, Height and Weight**

Weight (to be measured in street clothes, no shoes) and vital signs, including temperature, pulse, respiratory rate, and seated blood pressure, will be taken during the visits indicated in [Section 5](#).

Height will be recorded at Visit 1 only.

Vital signs will be obtained after the subject has been in a comfortable position for at least 5 minutes.

If body temperature is measured orally, since drinking hot or cold beverages (including water) has a significant impact on recorded oral body temperature, no beverages should be ingested within 15 minutes of the measurement. Investigators are to report any clinically significant abnormal findings as AEs.

